5. RESOURCES AVAILABLE TO CONDUCT THE HUMAN RESEARCH

- *Explain the feasibility of meeting recruitment goals of this project and demonstrate a potential for recruiting the required number of suitable subjects within the agreed recruitment period*
 - *How many potential subjects do you have access to?*
- *Describe your process to ensure that all persons assisting with the trial are adequately informed about the protocol and their trial related duties and functions*

The study will involve approximately 36 subjects with chronic hemiparesis following stroke. The research team will be led by [name], who has extensive experience recruiting for clinical trials related to stroke. Additionally, the Northwell Health System treats over 1000 patients with stroke annually, and provides an excellent recruitment population eligible for participation in this study.

The team in the Laboratory of Rehabilitation Robotics has substantial experience in the field of stroke rehabilitation. [name] is a treating neurologist, investigator, and lecturer with over 30 years of clinical and research experience with neurological recovery. [name] is a Physiatrist and Research Coordinator with over ten years of clinical experience in the treatment of neurological injuries and neurodegenerative impairment. [name] is a Research Coordinator and Speech-Language Pathologist with extensive clinical and research experience related to neurological injury. [name] is a Research Assistant with a background in neuroscience, and an expertise in EMG spike analysis.

Additionally, the team in the Center for Bioelectronic Medicine has extensive experience in engineering, programming, and clinical administration of vagus

nerve stimulation via tVNS devices. The team has developed a wireless all-in-one tVNS stimulator, the device was co-designed with an ISO 13485 certified company (MIDI), and fabricated by MIDI, and supplied to the CBEM team.

In order to ensure everyone assisting on the study is well versed in the protocol requirements, there will be a study team meeting after institutional approval is obtained. At this meeting, everyone will be reminded of the study design and all of the study processes. In addition, there will be a delegation of responsibility log created to outline the specific tasks of each study member during the course of the study. The study team will also routinely meet to discuss study progress and address any questions that arise.

6. RECRUITMENT METHODS

- *Describe the source of potential subjects*
- *Describe the methods that will be used to identify potential subjects*
- *Describe any materials that will be used to recruit subjects. A copy of any advertisements (flyers, radio scripts, etc.) should be submitted along with the protocol.*
- *If monetary compensation is to be offered, this should be indicated in the protocol*

Stroke subjects who meet inclusion criteria will be recruited by consenting professionals through the Departments of Physical Medicine and Rehabilitation, Neurology, and Outpatient Stroke Rehabilitation at NSUH, LIJMC, GCH, SSH, Transitions of Long Island, and STARs Outpatient Rehabilitation Center. Recruitment will be done with direct contact and flyers.

Northwell Health physicians and clinicians who have appropriate patient populations will be made aware of the research study protocol and procedures, and given an overview of the study through contacts with the study personnel. These clinicians will identify potential study participants, and either: 1.) provide the patient with the study coordinator's contact information or 2.) provide the patient's contact information to study personnel.

Investigators may contact (or be contacted by) a potential subject or subject's LAR/next-of-kin by telephone or email to discuss participation in this research protocol. The investigator will provide the subject/LAR/next-of-kin with all the information contained in the written consent form. The investigator will answer any questions regarding the research and give the subject/LAR/next-of-kin ample time to consider participation in the study which may require a follow-up phone conversation or an in-person appointment at the Feinstein for a brief study enrollment screening visit.

7. ELIGIBILITY CRITERIA

- Describe the characteristics of the subject population, including their anticipated number, age, ranges, sex, ethnic background, and health status. Identify the criteria for inclusion or exclusion of any subpopulation.
- Explain the rationale for the involvement of special classes of subjects, such as fetuses, pregnant women, children, prisoners or other institutionalized individuals, or others who are likely to be vulnerable. You cannot include these populations in your research, unless you indicate such in the protocol
- Similarly, detail exclusionary criteria: age limits, special populations (minors, pregnant women, decisionally impaired), use of concomitant medications, subjects with other diseases, severity of illness, etc.

Inclusion Criteria:

- Individuals between 18 and 85 years of age
- First single focal unilateral supratentorial ischemic stroke with diagnosis verified by brain imaging (MRI or CT scans) that occurred at least 6 months prior
- Cognitive function sufficient to understand the experiments and follow instructions (per interview with Speech Pathologist or PI)
- Fugl-Meyer assessment 12 to 44 out of 66 (neither hemiplegic nor fully recovered motor function in the muscles of the shoulder, elbow, and wrist).

Exclusion Criteria:

- Botox treatment within 3 months of enrollment
- Fixed contraction deformity in the affected limb
- Complete and total flaccid paralysis of all shoulder and elbow motor performance
- Prior injury to the vagus nerve
- Severe dysphagia
- Introduction of any new rehabilitation interventions during study
- Individuals with scar tissue, broken skin, or irremovable metal piercings that may interfere with the stimulation or the stimulation device
- Highly conductive metal in any part of the body, including metal injury to the eye; this will be reviewed on a case by case basis for PI to make a determination
- Pregnant or plan on becoming pregnant or breastfeeding during the study period
- Significant arrhythmias, including but not limited to, atrial fibrillation, atrial flutter, sick sinus syndrome, and A-V blocks (enrollment to be determined by PI review)
- Presence of an electrically, magnetically or mechanically activated implant (including cardiac pacemaker), an intracerebral vascular clip, or any other electrically sensitive support system; Loop recorders will be reviewed on a case by case basis by PI and the treating Cardiologist to make a determination

8. NUMBER OF SUBJECTS

- *Indicate the total number of subjects to be accrued locally. If applicable, distinguish between the number of subjects who are expected to be pre-screened, enrolled (consent obtained), randomized and complete the research procedures.*
- *If your study includes different cohorts, include the total number of subjects in each cohort.*
- *If this is multisite study, include total number of subjects across all sites.*

This is a double-blind, sham-controlled pilot study. The total target enrollment is 36 subjects with post-stroke hemiparesis. Only patients who meet inclusion criteria following screening will be enrolled. We have anticipated a 10-15% drop-out rate in determining target enrollment.

This study will use a randomized controlled study design to determine whether nine repeated treatments of upper extremity robotic therapy paired with tVNS delivered only during extensor movements significantly changes objective EMG activation patterns and significantly improves clinical measures of upper extremity motor function in patients with chronic post-stroke hemiparesis as compared to a sham condition.

9. STUDY TIMELINES

- *Describe the duration of an individuals participation in the study*
- *Describe the duration anticipated to enroll all study subjects*
- *The estimated date of study completion*

The duration of an individual's participation in the study is approximately 4 months from providing consent to completing the study procedures. It is anticipated that enrollment will be completed within 20 months from receiving institutional approval, with all study procedures completed within 2 years. After the completion of data analysis and any subsequent presentations or publications, the study will be closed. It is estimated that the study will be completed by December 2020.

10. ENDPOINTS

- *Describe the primary and secondary study endpoints*
- *Describe any primary or secondary safety endpoints*

The primary measure of treatment efficacy will be an increase in EMG activation peak amplitude for upper extremity extensor muscles of at least 10%. The secondary measure of treatment efficacy will be an improvement in Upper Extremity Fugl Meyer score of at least 3 points (out of 66).

The primary safety endpoint will be any serious adverse events of suspected relationship with the tVNS investigational device. Any serious adverse events will be reported to the PI, research team, and IRB immediately for determination if the study should be discontinued. However, given that there were no serious adverse device effects of implanted VNS in individuals with stroke [8], it is anticipated that transcutaneous auricular vagus nerve stimulation will pose an even lower risk.

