4. OBJECTIVE(S)/SPECIFIC AIMS AND HYPOTHESES

- *A concise statement of the goal(s) of the current study.*
- *The rationale for and specific objectives of the study.*
- *The goals and the hypothesis to be tested should be stated.*

Specific Aim 1: To evaluate whether 3 weeks of robotic therapy paired with tVNS delivered only during extensor movements will significantly change

EMG activation patterns of up the upper extremity during unassisted gravity-eliminated movements in approximately 18 patients with chronic post-stroke hemiparesis compared to sham condition.

In patients with chronic upper-limb hemiparesis post-stroke, we will use a within-subjects repeated measure design to determine if 9 sessions of active tVNS during only extensor movements significantly alters EMG activation of the biceps brachii and triceps as compared to a sham condition.

Specific Aim 2: To determine whether 3 weeks of robotic therapy paired with tVNS will significantly improve clinical measures of upper extremity motor function in approximately 18 patients with chronic hemiparesis after stroke compared to a sham condition.

We will use a within-subjects repeated measures design to determine if 9 sessions of robotic therapy paired with active tVNS during only extensor movements significantly improves upper extremity motor function in patients with chronic post-stroke hemiparesis as compared to sham tVNS paired with robotic therapy.

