11. RESEARCH PROCEDURES

- *Include a detailed description of all procedures to be performed on the research subject and the schedule for each procedure.*
- *Include any screening procedures for eligibility and/or baseline diagnostic tests*
- *Include procedures being performed to monitor subjects for safety or minimize risks*
- *Include information about drug washout periods*
- *If drugs or biologics are being administered provide information on dosing and route of administration*
- *Clearly indicate which procedures are only being conducted for research purposes.*
- *If any specimens will be used for this research, explain whether they are being collected specifically for research purposes.*
- *Describe any source records that will be used to collect data about subjects*
- *Indicate the data to be collected, including long term follow-up*

Consecutive Sessions of tVNS during robotic therapy intervention

Thirty-six patients with chronic, post-stroke upper extremity hemiparesis will be accepted into this study, and randomized to receive either sham or active tVNS treatment coupled with robotic therapy. There will be 2-3 baseline measurement periods prior to treatment. Following the lead-in period, subjects will participate in a training period consisting of approximately 1 hour sessions robotic therapy paired with tVNS 3x/week for 3 weeks, for a total of 9 sessions. Following the training period, subjects will complete clinical and objective measures both immediately at discharge and again a 3-month follow-up visit.

Lead-in Period

- Week 1, Visit 1 (approximately 90 minutes)
 - Baseline clinical outcome measures
 - Instrumental measures with EMG
 - Medical screening
 - Consent
- Week 1, Visits 2-3 (approximately 60 minutes each)
 - Baseline clinical outcome measures
 - Instrumental measures with EMG

Training Period

- Weeks 2-4, Visits 4-12 (approximately 60 minutes)
 - robotic therapy + tVNS

- Device tolerance questionnaires (every session)

Discharge Evaluation

- Week 4, Visit 13 (approximately 60 minutes)
 - Clinical outcome measures
 - Instrumental measures with EMG

Follow-Up Evaluation

- Week 16, Visit 14 (approximately 60 minutes)
 - Clinical outcome measures
 - Instrumental measures with EMG

**Phase II
Schedule**

	Screen 1	Screen 2	Screen 3	taVNS Tx + robotics	DC eval	3 mo FU
	Visit 1	Visit 2	Visit 3	Visit 4-12	Visit 13	Visit 14
Informed Consent	X					
Medical Hx	X					
Demographic Info	X					
Inclusion Criteria	X					

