12. STATISTICAL ANALYSIS

- *Describe how your data will be used to test the hypotheses.*
- *State clearly what variables will be tested and what statistical tests will be used.*
- *Include sample size calculations.*
- *If this is a pilot study, state which variables will be examined for hypothesis generation in later studies.*

For our primary outcome measure, we will investigate whether tVNS paired in a closed loop with robotic therapy changes peak amplitude EMG activation in muscle groups along the shoulder and elbow. We hypothesize that upper extremity flexor synergy will be significantly improved when active tVNS is applied during extensor movements as compared to a sham condition, and will lead to an increase in EMG peak activation at the triceps brachii (elbow extensor muscle). This will be examined with a 2x3 ANOVA with condition (active stimulation vs. sham) and time (peak amplitude of EMG activation during extensor movements at admission, discharge, and follow-up) as factors.

For our secondary outcome measure, we will test whether active tVNS during extensor movements paired in a closed loop with intensive robotic intervention (9 sessions) significantly improves upper extremity motor function as compared to sham tVNS paired with intensity-matched robotics. This will be examined with a 2x3 Friedman ANOVA with condition (active vs. sham tVNS) and time (upper extremity fugl meyer score at admission, discharge, and 3 month FU) as factors.

Since this is a pilot study, there are presently no data from which we can derive a power calculation. However, we propose to enroll 36 subjects, in order to achieve a target of at least fifteen subjects per treatment group and also allow for a 10-15% drop out rate. In our extensive past experience with upper limb hemiparesis rehabilitation studies, 10-15 subjects per treatment group is required at minimum to capture a measurable treatment response. Additionally, two other early pilot studies investigating post-stroke upper limb motor rehabilitation combined with VNS found a significant improvement in motor performance with nine and fourteen subjects per treatment group (e.g. sham and active VNS), respectively [8 & 41].

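### The 10% EMG criterion for primary efficacy is not tied to the active-versus-sham comparison, and the planned ANOVA does not state its deciding effect, leading visit or baseline rule

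*Combined protocol and SAP*

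**What the plan says.** Section 10 (Endpoints) gives the efficacy criteria. The primary one is "The primary measure of treatment efficacy will be an increase in EMG activation peak amplitude for upper extremity extensor muscles of at least 10" per cent. The secondary one is "an improvement in Upper Extremity Fugl Meyer score of at least 3 points (out of 66"). Neither sentence mentions sham, a visit, a baseline, or whether the threshold applies to a patient or to a group mean.

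Section 11 (Research Procedures) says patients are "randomized to receive either sham or active tVNS treatment coupled with robotic therapy", so robotic therapy is common to both arms. It also says: "There will be 2-3 baseline measurement periods prior to treatment". The schedule places EMG at Visits 1, 2 and 3, at discharge (Visit 13) and at 3 months (Visit 14).

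Section 12 (Statistical Analysis) asks whether tVNS "changes peak amplitude EMG activation in muscle groups along the shoulder and elbow" and hypothesises that, relative to sham, it "will lead to an increase in EMG peak activation at the triceps brachii (elbow extensor muscle"). The test follows: "This will be examined with a 2x3 ANOVA with condition (active stimulation vs. sham) and time", where time has the levels admission, discharge and follow-up. The 10% does not appear in Section 12. Aim 1 in Section 4 asks whether active stimulation "significantly alters EMG activation of the biceps brachii and triceps as compared to a sham condition", without a direction.

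**The concern.** A trial of tVNS added to robotic therapy has to show what tVNS contributes beyond the robot. Sections 2 and 3 say that robotic therapy alone improves motor impairment, so a rise in extensor EMG in both arms is plausible, although the documents do not quantify it. Applied to the active arm or to single patients, the 10% criterion would credit that shared rise to tVNS.

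Section 12 makes the right comparison but is not connected to the criterion. The two can give different answers, and the plan does not say which one counts as the primary result. Section 12 also leaves choices that could be made after the data are seen: the deciding effect, the leading visit, and the construction of the admission value.

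**Working it through.** **1. The plan's own figure.** Section 12 targets at least 15 per group, allows 10-15% dropout and enrols 36.
- 15% dropout: 15/(1 - 0.15) = 17.6, so 18 per group and 36 in total.
- 10% dropout: 15/(1 - 0.10) = 16.7, so 17 per group and 34 in total.

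The 36 is reproduced at the upper dropout rate. The 10% EMG criterion plays no part in it.

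**2. How often the criterion is met without a tVNS effect.** Inputs: n = 15 in the active arm (Section 12); threshold 10% (Section 10). Assumptions: a true percent change g equal in both arms, normal errors, and an SD of percent change of 20, 30 or 40 points.

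Group-mean reading: P = 1 - Φ((10 - g)/(SD/√15)). Single-patient reading: P = 1 - Φ((10 - g)/SD).

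| | SD 20 | SD 30 | SD 40 |
|---|---|---|---|
| Standard error, SD/√15 | 5.16 | 7.75 | 10.33 |
| z for g = 15 | -0.97 | -0.65 | -0.48 |
| Active-arm mean meets 10%, g = 15 | 83% | 74% | 69% |
| Active-arm mean meets 10%, g = 0 | 3% | 10% | 17% |
| A single patient meets 10%, g = 15 | 60% | 57% | 55% |

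The result depends on the unit, which Section 10 does not give.

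**3. The criterion against the planned test.** A 2x3 mixed ANOVA was simulated with 15 per arm and 10,000 trials per setting. Assumptions: baseline mean 100, between-patient SD 30, two-sided 5%, and the same change SDs. The criterion was read as the active-arm mean at discharge over its mean at admission.
- Both arms rise 15 points, no tVNS effect: the interaction is significant in about 5% of trials, as it should be. The criterion is met while the interaction is not significant in 79%, 70% or 64%.
- tVNS adds 10 points, no common rise: the interaction is significant in 26%, 13% or 10%. The criterion is met in about half, as it must be when the true gain equals the threshold.

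Disagreement in the other direction is also possible. For a single-visit contrast of log change with 15 per arm, an observed ratio of 1.10 reaches p < 0.05 only if the SD of log change is below ln(1.10)/(t(0.975, 28) × √(2/15)) = 0.0953/(2.048 × 0.365) = 0.127. Below that SD, a between-arm difference smaller than 10% can be significant.

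**4. What Section 12 leaves open.**
- Effect: the layout yields condition, time and interaction tests, and none is named as deciding.
- Visit: discharge and follow-up are both time levels, and neither leads.
- Baseline: admission is a time level, but no rule maps it to the two or three recordings before treatment.
- Muscle: triceps is named in the hypothesis, extensor muscles in Section 10, shoulder and elbow muscle groups at the start of the same Section 12 paragraph, and biceps and triceps in Aim 1.

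**The case against.** The strongest reply is that the intent is clear enough. Sham is the comparator in Sections 3, 4, 8 and 12. Section 12 names admission as the baseline level and triceps in the hypothesis. With a pre-treatment level in the time factor, the condition-by-time interaction is the natural test of differential change. A threshold for a meaningful change can properly stand beside a significance test, and this is a declared pilot.

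Much of this stands, and it rules out several stronger inferences that a reader might draw:
- *The trial has no comparator for its primary outcome.* It has one. Only the 10% criterion omits it.
- *The treatment effect will be diluted.* A 10% difference at both post-treatment visits averages to (0 + 10 + 10)/3 = 6.7% in the condition main effect. That matters only if the main effect decides, which is the strained reading.
- *The false-positive rate is 8-10%.* That figure assumes separate tests at two visits and a choice between them. The plan describes one ANOVA, and a single pre-named interaction test is not inflated by the number of visits.
- *The criterion is met half the time by chance.* That needs a true common gain of exactly 10% and symmetric errors. With no gain, the figure is 3-17% under the assumptions above.

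The objection does not supply the missing link. Nothing says how the 10% relates to the ANOVA, whether it applies to patients or groups, which post-treatment visit leads, or how the baseline recordings are combined. Pilot status explains the absent power calculation. It does not explain this gap, because Section 12 still tests a hypothesis against sham.

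**Conclusion.** The concern holds in this form: the Section 10 criterion is not linked to the Section 12 comparison, and as written it can be met with no tVNS effect. With a shared true rise of 15%, the active-arm mean meets it in about 83%, 74% or 69% of trials at SDs of 20, 30 or 40 points. The rise and the SDs are assumptions; that the criterion and the test can disagree does not depend on them. The unstated deciding effect, leading visit and baseline rule add to the problem but are secondary to it. The 3-point Fugl-Meyer criterion has the same gap, since it too names no comparator, visit or unit.

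This should be fixed, because applying the stated criterion could give a wrong conclusion about tVNS. Two wording points in Section 11 are minor clarifications and not part of the claim: the primary label on Fugl-Meyer, which may only mean the lead clinical scale, and the statement that EMG is recorded in stimulation sessions when the schedule puts it at evaluation visits.

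**What to change.** In Sections 10 and 12:
- Make the primary contrast the active-versus-sham difference in triceps brachii peak EMG during extension at one pre-named visit, for example discharge (Visit 13).
- Adjust for the mean of the available pre-treatment recordings.
- Fix one scale in advance, for example log, reported as a ratio, with a 95% CI and a stated two-sided alpha.
- Keep the 2x3 ANOVA as supportive, with the condition-by-time interaction named as its test of interest.
- State that the 10% and 3-point thresholds are descriptive, or are between-arm reference values, and are not within-arm success rules.

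No new visits or recordings are needed, but the primary analysis changes from the ANOVA to a single contrast. Other muscles and the follow-up visit become secondary and can no longer carry the primary claim.

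Precision will be limited. With 15 per arm, the 95% CI is the estimated ratio multiplied or divided by exp(2.048 × SD × √(2/15)). For an assumed SD of log change of 0.10, 0.20, 0.30 or 0.40, that factor is 1.08, 1.16, 1.25 or 1.35. Power for a true ratio of 1.10 (noncentral t, 28 df, two-sided 5%) is about 71%, 24%, 13% or 10%. The trial may therefore be unable to resolve a 10% difference, and the report should rest on the interval.

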Electrical activity of the muscle will be differentially recorded during tVNS sessions using a bipolar electrode montage placed on the belly of the muscle. Recordings will be made from the biceps and triceps brachii, pectoralis major, rhomboideus, and/or the deltoids, which are some of the important muscles responsible for flexion and extension of the shoulder and elbow.

Randomization

Subjects will be stratified by established clinical impairment levels based upon admission Upper Extremity Fugl Meyer scores (low function <23 & moderate function 23-44) such that there are an equal number of low and high functioning patients in each treatment group. Subjects will then be randomized to either the active or sham tVNS group [28]. Assignment will be predetermined by a randomized assignment list, created prior to the enrollment of the first subject by an investigator from the CBEM team who is not directly involved in subject treatment. There will be concealed allocation of treatment assignment such that investigators involved in subject screening, consent, and clinical scoring will be blinded to treatment condition.

Blinding

This will be a double-blind pilot study in which subjects will be randomly assigned to either the sham or active tVNS conditions. Subjects will be told that they have a 50-50 chance of receiving either active or sham stimulation, but they will not be told which condition they receive. Additionally, the assigned clinical evaluators will remain blinded to condition. For each study session, stimulation condition will be programmed into the device by the RA or members of the CBEM team who are not performing clinical measures.

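### Sections 4, 10 and 12 define the primary EMG measure on different muscles, and the planned ANOVA has no rule for choosing or combining them

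*Combined protocol and SAP*

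**What the plan says.** Four statements describe the primary EMG measure:

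- **Section 4, Aim 1:** the question is whether active tVNS "significantly alters EMG activation of the biceps brachii and triceps as compared to a sham condition". This covers one flexor and one extensor, with no direction.
- **Section 10:** the measure is "an increase in EMG activation peak amplitude for upper extremity extensor muscles", and the increase must be at least 10%. The extensors are not listed.
- **Section 12, opening sentence:** the primary outcome asks whether the treatment "changes peak amplitude EMG activation in muscle groups along the shoulder and elbow". The set is broad and no direction is given.
- **Section 12, hypothesis:** the expected effect is an "increase in EMG peak activation at the triceps brachii (elbow extensor muscle"), so one muscle and one direction.

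The test is a "2x3 ANOVA with condition (active stimulation vs. sham) and time". Its variable is peak amplitude during extension movements at admission, discharge and follow-up.

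Separately, the electromyography paragraph of Section 11 lists what is recorded: "biceps and triceps brachii, pectoralis major, rhomboideus, and/or the deltoids".

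**The concern.** A 2x3 ANOVA on condition and time takes one amplitude per patient and visit. If several muscles are recorded, someone must decide whether to use one of them, average them, or run the model once per muscle. The plan does not say which, and its statements of the primary measure point to different answers. An analyst who runs the model on both Aim 1 muscles is following the protocol. So is one who runs it on triceps alone.

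What is at stake is the meaning of a significant primary result. If two or more muscles are tested and any one can be reported as primary, the error rate of the primary claim exceeds that of each test. A reader of the results could not tell from the protocol whether the reported muscle was fixed beforehand.

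**Working it through.** **1. The statements side by side**

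| Place | Muscles | Direction | Movement |
|---|---|---|---|
| Section 4, Aim 1 | biceps and triceps | none | unassisted, gravity removed |
| Section 10 | extensors, not listed | increase, at least 10% | not stated |
| Section 12, opening | shoulder and elbow groups | none | not stated |
| Section 12, hypothesis | triceps | increase | extension |

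Triceps is the one muscle that fits all four rows. Biceps fits the first and third only. The movement task also differs between Section 4 and Section 12.

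**2. The plan's own figure.** Section 12 wants at least 15 per group and allows 10-15% dropout. At 15%, 15 / 0.85 = 17.6, so 18 per group and 36 in total, as stated. At 10%, 15 / 0.90 = 16.7, so 17 per group and 34 in total. The 36 does not depend on which muscle is primary and is not in question here.

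**3. Error rate if k muscles are tested.** Assumptions: two-sided 5% per test (neither alpha nor sidedness is stated), one contrast per muscle, and no true effect.

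If the tests are independent, P(at least one false positive) = 1 - 0.95^k:

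- k = 2 (Aim 1): 1 - 0.95^2 = 9.75%
- k = 5 (every muscle or group in the Section 11 list): 1 - 0.95^5 = 22.6%

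Muscles in one arm are likely to be correlated, and the documents give no correlation. The correlated cases were simulated as two-sample t-tests with 15 per group, a common between-muscle correlation and 20,000 runs. The Monte Carlo standard error near 10% is sqrt(0.1 x 0.9 / 20,000), or 0.2 percentage points.

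| Assumed correlation | 2 muscles | 5 muscles | 5 muscles, increases only |
|---|---|---|---|
| 0 | 10.1% | 22.7% | 12.0% |
| 0.3 | 9.0% | 21.1% | 11.0% |
| 0.5 | 8.8% | 18.9% | 9.3% |
| 0.7 | 8.3% | 15.2% | 7.7% |
| 0.9 | 7.4% | 10.4% | 5.2% |

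The last column counts only significant increases, and its single-test reference is 2.5%. For two muscles counted that way, the range is 5.0% (correlation 0) to 3.6% (correlation 0.9). The zero-correlation row agrees with the formula within simulation error.

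**4. Naming one muscle or adjusting for several.** With 15 per group and 80% power, the detectable standardised difference is about 1.06 for one test at 5%. With Bonferroni it is about 1.18 for two muscles (2.5% each) and 1.33 for five (1% each). At a true difference of 1.06, power falls from 80% to 70% and 56% respectively. In a trial this small, one primary muscle preserves the most power.

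**The case against.** The best defence is that Section 12 already designates triceps. It moves from a general question to a triceps hypothesis, and the next sentence says this will be examined by the ANOVA. That is the natural reading, and it is why triceps is the right muscle to name. It does not settle the matter. The test sentence identifies its variable by movement, and any recorded muscle has an amplitude during extension. Section 10 does not say triceps, and Aim 1 gives biceps equal standing.

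A reader might infer that a positive result in any recorded muscle could be claimed as the primary result. The documents do not support that. Section 10 requires an increase in extensors, so a biceps or pectoralis finding would not meet it. Only the opening sentence of Section 12 is broad enough to admit the whole list.

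A reader might also treat Section 11's list as a further endpoint definition, or infer from its wording that different patients will contribute different muscles. Neither follows. The list is a recording montage, said to apply during tVNS sessions (Visits 4-12), whereas the schedule places the instrumental assessments at Visits 1-3, 13 and 14. It may be the montage intended for those visits, since no other is given. The and/or can also be read as leaving biceps and triceps always recorded.

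Finally, this is a pilot, which lowers the stakes. It still states a primary efficacy measure and a significance test. The Section 12 template asks which variables will be tested and, for a pilot, which serve hypothesis generation. The plan does not make that separation for the muscles.

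**Conclusion.** The inconsistency is in the text and does not depend on any calculation: Sections 4, 10 and 12 put the primary EMG measure on different muscles, and the ANOVA has no rule that resolves the difference. More than one muscle can therefore be tested and read as primary.

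For Aim 1's two muscles, the chance of at least one false-positive primary result is about 8-10% over correlations of 0 to 0.7. The range of about 15-23% for five muscles is a worst case. It requires Section 12's broadest sentence, the whole Section 11 list, five separate tests and credit for either direction. If only increases count, five muscles give about 8-12% over the same correlations, against 2.5%. All of these figures rest on an assumed two-sided 5% per test and on assumed correlations.

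The sample size is unaffected. The wording should be aligned before any EMG data are analysed.

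**What to change.** - **Sections 4, 10 and 12:** name triceps brachii peak amplitude, the muscle in Section 12's own hypothesis, as the single primary EMG measure.
- **Movement task:** state one task in all three sections, reconciling Aim 1's unassisted, gravity-eliminated task with Section 12's extension movements.
- **Contrast:** name one ANOVA effect as primary, for example condition by time from admission to discharge, with its significance level and sidedness. Naming the muscle alone would not leave a single primary test.
- **Other muscles:** label biceps and all the rest secondary or exploratory.
- **Section 11:** state that triceps and biceps are recorded at every EMG assessment visit (baseline, discharge and follow-up), and apply the and/or only to the remaining muscles.

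The cost is wording in four sections. Triceps and biceps are already on the recording list and the EMG visits are already scheduled, so no visit is added. The real loss is that Aim 1's biceps result is no longer primary, which narrows that aim. If the investigators want both muscles as primary, the alternative is a stated multiplicity adjustment, at the loss of power shown above.
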